3.6.1. Effect size

Primary Outcomes:

- Preoperative change in hemoglobin concentration (g/dL) and change in serum ferritin (mcg/L), which is, the difference between the value at diagnosis and preoperative day.

Secondary Outcomes:

- Units of red blood cells transfused in perioperative period in the two groups, defined as:
 1. Preoperative - from randomization to operation;
 2. Intraoperative – inside operating theatre and recovery room;
 3. Postoperative - from arrival to ward after operation to discharge.
- Duration of hospital stay (days).
- Quality of recovery as measured by questionnaire (QoR-15(Chinese)) completed on postoperative period. The QoR-15 (See Appendix A) includes the items measuring pain, physical comfort, physical independence, psychological support and emotional state.¹³ The QoR-15 score ranges from 0 to 150 and takes about 3 minutes to complete.¹³ The validity (convergent, construct, discriminant), reliability (internal consistency, split-half, test-retest), responsiveness,

acceptability and feasibility properties have been well established.¹³

- Incidence of adverse reactions/serious adverse events to intravenous iron administration and adverse reaction to blood transfusions (Adverse reactions: any unintended responses related to drug/blood products administrations e.g. skin rash, pain, neurological/respiratory/cardiovascular symptoms. Serious adverse events: life-threatening/require additional period of hospitalization/results in disability/mortality eg. Anaphylaxis, acute hemolytic transfusion reactions, organ failure etc.).
- Rate of surgical complications recorded and graded according to Clavien Classification of Surgical Complications.¹⁴ (See Appendix B)
- Days (alive and) at home within 30 days of surgery (DAH₃₀)
 - A parameter incorporating the duration of initial hospital stay associated with the index surgery, re-hospitalization due to post-discharge complications, discharge to institutional care and early deaths within 30 days post operatively. It has been validated as an effective patient-centered outcome measure for perioperative trials.¹⁵
 - Method of calculation – refer to Appendix C

3.6.2. Study process:

- Patient recruitment rate (number of recruited patient/total number of eligible patients x 100%)
- Number of patients recruited per month.
- Median waiting time to surgery (days).

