3.7. Randomization, allocation concealment and blinding

Recruited patients would be prospectively randomized to either preoperative intravenous iron isomaltoside (treatment group) or standard care (control group). The 1:1 allocation will be performed by one of the investigators, not involved in patient care or study assessment, using a computer program PASS 14.0 (NCSS, Kaysville, UT). The treatment allocation will be concealed in sealed opaque envelopes and handed over to third party anaesthetists (other than the investigators) for arranging pre-operative

intravenous iron therapy for patients in the treatment arm, or no therapy in the control arm.

Records related to the iron administration will be kept away from the investigators and the parent surgical team for the duration of the study period to reduce performance bias. Patients in both arms will not be blinded to the treatment they may receive in the management of perioperative anaemia, be it intravenous iron in the treatment group, or any necessary perioperative blood transfusions in either groups. An alert in the patient's electronic records will be implemented to remind the parent surgical team and the case anaesthetist that the patient is participating the study, however the both parties will be blinded to the patients' group assignment, to avoid interference to their transfusion decision.

Unblinding will be done only in the condition where clinician believes that clinical management depends importantly on whether the patient received intravenous ferric isomaltoside. Unblinding will be achieved by contacting the investigators, and any unblinding event and the reason of unblinding will be recorded.

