3.8. Baseline patient demographics and clinical data collection

After patient recruitment, baseline characteristics including age, sex, body weight and height, ASA grading, important past health comorbidities (hypertension, diabetes mellitus, significant cardiovascular diseases, known hemolytic conditions/hemoglobinopathy), medication history will be collected. The information regarding baseline hematological profile (hemoglobin level, ferritin level) at the time of recruitment will be recorded.

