3.9. Standard perioperative care apart from the study interventions

Standard anaesthetic preoperative assessment will be carried out either in the preoperative assessment clinic or by the list anaesthetist on the day before surgery, according to the routine practice in our hospital for all elective colorectal cases. Patients are allowed to continue their usual medications as directed by the parent surgical team and case anaesthetists. Upon recruitment, patients will not receive iron supplements other than intravenous iron isomaltoside.

Following the existing practice, patients for elective colorectal cancer resection operations are admitted to surgical wards one day before the operation. The second batch of study blood tests (including complete blood count, iron profile) will be taken along with cross match on admission. Bowel preparation will be undertaken if deemed necessary by the parent team.

General anaesthesia will be provided by anaesthetists blinded to the study allocation, without restrictions on the anaesthetic agents and analgesic modalities to be used. As per usual practice within the department, intravenous induction will be achieved with propofol and fentanyl, followed by maintenance with sevoflurane/desflurane. Muscle relaxation with non-depolarizing muscle relaxant (atracurium/cisatracurium/rocuronium) will be maintained throughout the operation, followed by reversal with neostigmine/atropine at the end of operation. Analgesia will be achieved by multimodal approach, by a combination short and long acting opioids (fentanyl/morphine), tramadol, paracetamol, non-steroidal anti-inflammatory drugs (NSAIDs) and local anaesthetics (intravenous infusion and/or local infiltration) at the discretion of the list anaesthetists. Antiemetics will be given as routine either with ondansetron, dexamethasone or metoclopramide.

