3.10. Intervention: intravenous iron isomaltoside(Monofer®)

Patients randomized to the treatment group will be given a dose of intravenous iron isomaltose in the time frame of 3-10 weeks before operation date. The dose will be determined by the patient's body weight: > 50kg: 1000mg; <50kg: 20mg/kg body weight, to be infused over 30 minutes. The infusion would take place in the day surgical unit and patients will be closely monitored. Vital signs would be charted before, at 15 minutes during infusion and immediately after the infusion. Patients will be discharged home on the same day if no adverse reactions are observed.

2 weeks after intravenous iron isomaltoside administration, blood test for hemoglobin level and iron profile would be repeated. Subjects with hemoglobin level less than 10g/dL will receive a second dose of intravenous iron isomaltoside. The second dose would be identical to the first dose i.e. body weight: > 50kg: 1000mg; <50kg: 20mg/kg body weight, to be infused over 30 minutes. Similar as before, intravenous iron administration would take place during a day admission to the day surgical unit with monitoring.

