3.12. Follow up/assessment

Data on the primary and secondary outcomes as listed above would be collected. Investigators will access the patients' records via the Hospital Authority computer system and the hardcopy documents in the wards. Data on the hematological profile throughout study period (on diagnosis, preoperative day, post-operation day one, on discharge) will be retrieved from the computer records. The number of red cell transfusion will be retrieved from the computer records as well as counterchecking with

anaesthetic records/progress notes. The length of hospital stay (for the operation and DAH₃₀) will be counted by referring to computer patient records.

The quality of recovery is assessed by a self-reported quality of recovery questionnaire (QoR-15)¹³, which assess different dimensions of recovery including pain, physical comfort, physical independence and mental well-being.

4. Statistical analysis

Missing data will be checked and imputed to preserve power. The Shapiro-Wilk test will be used to check data for normality. Generalized estimating equations will be used to examine the changes in haemoglobin level and serum ferritin levels over time. Expected skewed data, such as the quality of recovery score, the number of days of hospital stay, units of transfusion and DAH₃₀, will be reported as median and interquartile range, and compared between treatment arms by Mann-Whitney U tests. Two-tailed χ^2 test will be used to analyze categorical data between groups. All of the analysis would be intention-to-treat and with a statistical significance level defined at $P < 0.05$.

5. Expected impact on study/patient care

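### Section 3.7 means the investigators not to know who received iron, but section 3.12 does not keep complication grading apart from iron results that are likely to suggest the arm

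*Combined protocol and SAP*

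**What the plan says.** **Masking (3.7).** "Records related to the iron administration will be kept away from the investigators and the parent surgical team", for as long as the study runs; the reason given is performance bias. The investigator who performs the allocation is kept out of patient care and study assessment. Patients are not blinded. A clinician who needs to know the arm asks the investigators.

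**Data collection (3.12).** For the outcome data, investigators are to reach the patients' "records via the Hospital Authority computer system and the hardcopy documents in the wards". On laboratory results: "Data on the hematological profile throughout study period (on diagnosis, preoperative day, post-operation day one, on discharge) will be retrieved from the computer records". Section 3.8 shows what such a profile contains, since it speaks of the "baseline hematological profile (hemoglobin level, ferritin level) at the time of recruitment".

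**When iron profiles are drawn (3.9, 3.10).** Patients are admitted the day before surgery: "The second batch of study blood tests (including complete blood count, iron profile) will be taken along with cross match on admission". Another iron profile is taken on postoperative day 1. In the treatment section only: "2 weeks after intravenous iron isomaltoside administration, blood test for hemoglobin level and iron profile would be repeated". The infusion is a day surgical unit visit. Section 3.11 describes neither for controls.

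**Outcomes that need judgement (3.6.1).** "Rate of surgical complications recorded and graded according to Clavien Classification of Surgical Complications", together with adverse reactions to intravenous iron and to transfusion. No grader is named and no order of extraction is given.

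**The concern.** The allocating investigator is kept out of assessment and the other investigators are denied the administration records, so the plan evidently wants outcomes assessed without knowledge of the arm. Withholding the infusion record does not achieve this if the same people read the laboratory consequence of the infusion. Change in ferritin is a primary outcome, so the admission ferritin has to be retrieved for every patient.

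Detection bias in the complication rate is at stake. Whether a minor departure from normal recovery is written down as a complication is a judgement made from notes, and a grader who suspects the arm may make it differently in the two groups. Section 3.7 names performance bias and transfusion decisions as its targets; it does not address outcome assessment. Section 3.1 describes the pilot's design as the same as that of the proposed larger trial, so the gap could carry forward.

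**Working it through.** The plan gives no figure on this point to reproduce. The check sets the sections side by side and then asks how strong the laboratory cue is likely to be.

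**1. Access**

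| Information | Who has it | Section |
|---|---|---|
| Iron administration record | withheld from investigators | 3.7 |
| Preoperative and day-1 iron profile | drawn in all patients; haematology series retrieved from computer records | 3.9, 3.12 |
| 2-week iron profile | treated patients only; not among the four retrieval points listed | 3.10, 3.12 |
| Day-unit visit | treated patients only; visibility to investigators not stated | 3.10 |
| Clavien grading | grader and timing not stated | 3.6.1, 3.12 |

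No section masks laboratory values, names a blinded grader, or puts grading before laboratory retrieval.

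**2. Haemoglobin alone is a weak cue.** The Background cites a trial with median rises of 1.55 g/dL (IQR 0.93 to 2.58) on intravenous iron and 0.5 g/dL (IQR -0.13 to 1.33) on oral iron. With a normal approximation and SD = IQR width / 1.349:
- SDs are 1.65/1.349 = 1.22 and 1.46/1.349 = 1.08 g/dL.
- AUC = Φ(1.05/√(1.22² + 1.08²)) = 0.74.
- The root-mean-square SD is √((1.22² + 1.08²)/2) ≈ 1.15. A midpoint cut then guesses the arm correctly with probability Φ(1.05/(2 × 1.15)) ≈ 0.68.

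The comparator there was oral iron, so this is only indicative.

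**3. Ferritin is likely to be a stronger cue.** At entry it is below 30 mcg/L, or 30 to 100 mcg/L with TSAT below 20% (3.3). After recruitment no other iron is given (3.9). The Background states that serum ferritin tracks body iron and puts total body iron at about 3500 mg, two-thirds in haemoglobin and 20% in stores.
- Normal store: 0.20 × 3500 = 700 mg. One 1000 mg dose is 1000/700 = 1.4 stores.
- Haemoglobin iron: 3500 × 2/3 = 2333 mg. Assuming a normal haemoglobin of 13 to 15 g/dL, each 1 g/dL holds 2333/13 = 179 mg to 2333/15 = 156 mg.
- A rise of 1.55 g/dL then uses 278 to 241 mg and leaves 722 to 759 mg, or 1.03 to 1.08 normal stores, in patients who entered depleted.

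A clear ferritin rise in the treated arm only is therefore expected. Its size is not in the documents. If the arms are d standard deviations apart, the share of correct guesses is Φ(d/2):

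| assumed d | 1 | 2 | 3 | 4 |
|---|---|---|---|---|
| correct guesses | 69% | 84% | 93% | 98% |

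**4. Which outcomes are exposed.** Laboratory values, deaths, transfused units, hospital stay and DAH30 are measured or counted. QoR-15 is self-reported by patients who know their arm. In Appendix B, grade II depends on treatment given, grade III on an intervention, grade IV on intensive care management and grade V on death. Grade I has no such anchor, so the exposure is mainly there.

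**5. Size.** The documents give no complication rate. By way of illustration, if suspicion of the arm changes the classification of 1 or 2 of 20 patients in one arm, the between-arm difference moves by 1/20 = 5 or 2/20 = 10 percentage points. If both arms shift in opposite directions, it moves by 10 or 20.

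**The case against.** The strongest reply is that the plan is silent here, not shown to be unblinded. Section 3.12 does not say who grades complications or that grading follows laboratory retrieval. The 2-week test, the one laboratory result described only for treated patients, is not on its retrieval list, and infusion records are what section 3.7 withholds. No post-infusion ferritin is given. From grade II upward the Clavien grade rests on care decided by clinicians whom section 3.7 also blinds. This is a 40-patient pilot with laboratory primary outcomes, and section 5 sizes the larger trial from the primary effect sizes, not from complications.

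Most of this stands, and it limits the point. A reader might infer that the hospital record reveals the arm outright, so that all complication and event assessment is in practice unblinded. The documents do not support that: the preoperative and day-1 results are a probable cue of unknown strength, and visibility of the day-unit visit or 2-week test is an assumption. A reader might also infer that recording of reactions to intravenous iron could be blinded. It cannot, because only one arm receives it. Nor is carry-over to the larger trial certain, since section 5 says that the pilot will help refine its design.

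The objection does not remove the gap. The preoperative ferritin is on the retrieval list, and no rule keeps it from whoever grades.

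**Conclusion.** The concern holds in a limited form. Sections 3.7 and 3.12 together do not deliver the masking of investigators that section 3.7 intends, and Clavien grading, chiefly whether grade I events are recorded, is open to detection bias. This rests on two inferences: that ferritin separates the arms enough to be noticed, which entry ferritin, dose and untreated controls make likely; and that those who grade may see iron results first, which nothing prevents. The amount of bias cannot be estimated from the documents; the 5 to 20 point shifts are illustrations only. The primary outcomes, and the sample size to be based on them, are little affected. The change is worth making because it is cheap and because a bias in recorded grades is hard to undo later.

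**What to change.** - **3.12, grading.** State that, for each patient, Clavien complications are graded and locked from the records of the surgical admission and later, before the grader opens any post-randomisation iron profile or day-unit record. Baseline values used for eligibility can still be seen.
- **3.12, laboratory data.** State that the haemoglobin and ferritin series is exported only after that lock.
- **3.12, transfusion.** Keep the full window of section 3.6.1, which begins at randomisation. Infusion is planned 3 to 10 weeks before surgery and admission is one day before, so starting at admission would lose most of the preoperative window. Extract units given before the surgical admission after the lock.
- **3.7.** State that adverse reactions to intravenous iron are recorded unblinded, because only one arm receives it.

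The cost is wording and a different order of data entry; no visit, test or extra staff is needed. Laboratory data are compiled later, and records with transfusions before the surgical admission are opened a second time. Mentions of iron in ward notes or discharge summaries may still unblind some patients, so the change reduces the bias but does not remove it.

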3.4. Exclusion criteria (None of the criteria must be fulfilled)

- Pregnancy or lactation
- Other known causes of anaemia apart from iron deficiency: untreated B12/folate deficiency, hemolytic disease, hemoglobinopathy/thalassemia, chronic renal failure on dialysis
- Presence of iron overload (serum ferritin > 300g/dL or TSAT > 50%); known hemochromatosis
- Previous or ongoing iron replacement/use of erythropoietin within 12 weeks before recruitment
- Known hypersensitivity towards iron isomaltoside
- Significant liver function derangement (AST/ALP exceeding three times upper

limit of normal range)

- Use of preoperative immunosuppressant therapy
- Participation in another ongoing interventional clinical trial(s)
- Patients with less than 3 weeks waiting time to surgery

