6.1. Safety profile of iron isomaltoside (Monofer®)

Among the six currently available formulations of intravenous iron available, serious adverse events are very rare (38 per 10⁶ administrations). About 1:200 patients receiving intravenous iron experience complement activation related pseudo-allergy which manifests as arthralgia, myalgia and flushing, which should not be confused with true anaphylaxis. These symptoms typically subside without interventions.² There are concerns on the effects of oxidative stress caused by intravenous iron but there is no evidence of clinical adverse event resulting from it. Some suggested that intravenous iron may promote infection by providing iron to pathogenic bacteria¹⁶, however there is no increase in infection observed in a meta-analysis of 103 trials published from 1965 to 2013 (including 19,253 patients).¹⁷

Study subjects would be given an information card with study title and contact information of the investigators (See Appendix D). Subjects would be advised to bring along the card with them, such that subjects or their medical practitioners can contact the investigator via the phone number on the card if problems or queries arise during the study period.

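### Section 3.10 requires an identical second dose on haemoglobin alone, with no stated exception for a reaction to the first, and Section 3.7 masks the iron records without naming anyone to pass a reaction on.

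*Combined protocol and SAP*

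**What the plan says.** **Second dose.** Section 3.10 repeats the blood tests two weeks after the infusion and then states: "Subjects with hemoglobin level less than 10g/dL will receive a second dose of intravenous iron isomaltoside". That dose is to be the same as the first. Haemoglobin is the only condition given.

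**Hypersensitivity.** Section 3.4 lists "Known hypersensitivity towards iron isomaltoside" among the exclusion criteria. Section 3.10 does not apply it again before the second dose.

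**Monitoring.** Section 3.10 places the infusion in the day surgical unit under close monitoring: "Vital signs would be charted before, at 15 minutes during infusion and immediately after the infusion". Same-day discharge depends on no reaction having been seen.

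**Masking.** Third-party anaesthetists, who are not investigators, arrange the infusions (3.7). The same section says "Records related to the iron administration will be kept away from the investigators and the parent surgical team for the duration of the study period", and gives reduction of performance bias as the reason. The case anaesthetist is also masked; Section 3.9 repeats that "General anaesthesia will be provided by anaesthetists blinded to the study allocation". Patients are not masked.

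**Ways through the masking.** Section 3.7 allows this: "Unblinding will be done only in the condition where clinician believes that clinical management depends importantly on whether the patient received intravenous ferric isomaltoside". The route is: "Unblinding will be achieved by contacting the investigators, and any unblinding event and the reason of unblinding will be recorded". Under Section 6.1, patients carry a card so that "subjects or their medical practitioners can contact the investigator via the phone number on the card".

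**Outcome.** Adverse reactions and serious adverse events to intravenous iron are a secondary outcome (3.6.1).

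**The concern.** Two rules that are sensible for an uneventful infusion are written as if every infusion will be uneventful.

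The first is the re-dosing rule. A patient who reacts to the first infusion and still has haemoglobin below 10 g/dL two weeks later meets the only stated condition for an identical repeat. Staff who withheld it would be departing from the written text.

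The second is the path of information. The person most likely to see a reaction is outside the investigator group, and the records of the infusion are withheld from the investigators and the surgeons. If nobody is told to report, three parties may not hear of a reaction in time: the team about to anaesthetise and operate on the patient, the investigators while other patients are still being infused, and whoever must count reactions for the 3.6.1 outcome.

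**Working it through.** This is mainly a reading of the text. The arithmetic only sets the scale. The plan gives no figure on this point to reproduce.

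**1. Is there a condition on the second dose other than haemoglobin?** No. Section 3.10 uses mandatory wording with a haemoglobin threshold. The hypersensitivity criterion in 3.4 governs entry. No section links the two.

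**2. Who would learn of a reaction, and how?**

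| Safeguard | Where | What it does | What it leaves open |
|---|---|---|---|
| Monitoring, discharge only if no reaction | 3.10 | Staff must look for reactions | What to record beyond vital signs, and whom to tell |
| Unblinding on clinical need | 3.7 | A clinician who asks can learn the arm | Someone must first think to ask; the request goes to investigators from whom the iron records are withheld |
| Contact details and card | 3.5, 6.1 | Patient or doctor can phone | Depends on a call being made |
| Unmasked patient, preoperative assessment | 3.7, 3.9 | The patient can mention a reaction | Depends on the patient doing so |
| ICH-GCP commitment | 8 | General undertaking | Names no reporter, recipient or timing |

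A patient kept in hospital after a reaction could meet the serious-event definition in 3.6.1, which includes an additional period of hospitalisation. No onward step is written even for that case. Section 3.12 says that all listed outcomes will be collected, and describes how haematology, transfusion, length of stay and quality of recovery are obtained. It names no source for iron reactions.

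**3. How often might it matter?** Inputs from the documents: 20 treated patients (3.1); serious events at 38 per million administrations, for six formulations together; pseudo-allergy in about 1 of 200 patients (both 6.1). The chance of at least one event in n is 1 − (1 − p)^n.

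- Serious, one dose each: 1 − (1 − 0.000038)^20 = 0.076%, about 0.08%.
- Serious, if all 20 were re-dosed (upper limit, 40 infusions): 1 − (1 − 0.000038)^40 = 0.15%.
- Pseudo-allergy: expected 20 × 0.005 = 0.1 patients; 1 − 0.995^20 = 9.5%. Section 6.1 says that these symptoms typically settle untreated and should not be confused with anaphylaxis, so this is not a rate for the reactions that matter here.
- Re-dosed after a serious first-dose event, assuming that half of treated patients are below 10 g/dL at two weeks, independently of reacting: 20 × 0.000038 × 0.5 = 0.0004 patients expected.

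**4. Other hypersensitivity.** The documents give no rate. Purely as an assumed range, let p be 0.5% to 5% per patient and let q, the share below 10 g/dL at two weeks, be 10% to 50%, independent of reacting.

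- Patients with a reaction: 20p = 0.1 to 1.0; chance of at least one, 9.5% to 64%.
- Patients re-dosed after one: 20pq = 0.01 to 0.5; chance of at least one, 1 − (1 − pq)^20 = 1.0% to 39.7%.

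The upper ends need a 5% reaction rate, and the last figure also needs half of patients to qualify for re-dosing. Neither figure comes from the documents.

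**The case against.** The strongest reply is that the plan has more protection than these two sentences suggest. Infusions are closely monitored and discharge depends on the result. Patients know their arm, can tell any doctor that they reacted, and would be present to say so before a second infusion. An anaesthetic assessment precedes surgery. The unblinding clause could be triggered by a reaction. The masking serves to limit performance bias and need not be read as hiding a clinical note of a reaction, given that investigators have the hospital computer records and ward documents (3.12). Any anaesthetist would be expected to withhold iron from a patient who had reacted badly to it.

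Much of this stands, and it rules out two stronger readings that a reader might infer:

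- *That the protocol orders re-dosing after a reaction.* It does not. Section 3.10 is silent on reactions; the fault is that a mandatory rule fails to exclude the case.
- *That reactions are sealed off from the treating team and investigators with no exception.* They are not. Section 3.7 has a clinical-need unblinding route, and patients can speak for themselves.

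What does not stand is that these safeguards make a written rule unnecessary. Each depends on someone choosing to ask, tell, or depart from the text. The objection also fairly notes that unblinding for every loosely suspected reaction would erode the masking. Section 3.9 sets no transfusion trigger, so masking is the stated protection for that decision. The change should therefore be narrow.

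**Conclusion.** The point holds as two specific gaps. First, the second-dose rule is mandatory on haemoglobin alone and states no exception for a reaction to the first dose. Followed literally, it could re-expose a patient who reacted. This is the firmer part and stands by itself. Second, iron records are masked with only a general unblinding route on request, and no section says who passes on a reaction seen at the infusion. The existing safeguards are partial and passive.

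The expected number of events is small. The documented rates support a 0.08% chance of any serious event among 20 infusions, and 0.1 expected cases of pseudo-allergy that usually settles. A reader might take the assumed upper figures of 64% and 40% as forecasts; the documents do not support that. The reason to act is the consequence for an individual patient set against the low cost. Because Section 3.1 gives the pilot the same design as the larger trial, the same wording would also carry forward to more infusions.

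No sample size, analysis or primary outcome changes. The conclusion rests on the protocol text; the patient information sheet was not reviewed and may say more.

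**What to change.** **Section 3.10.** Add: no second dose after a serious adverse event (as defined in 3.6.1) or a hypersensitivity reaction to the first dose. Mild, self-limiting pseudo-allergy as described in 6.1 is left to the third-party anaesthetist's judgement.

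**Section 3.7.** Exempt serious adverse events and hypersensitivity reactions from the masking, with the same exclusion for mild pseudo-allergy. The third-party anaesthetist reports them the same day to the investigator who performs the allocation, who is not involved in care or assessment, and to the treating team. Log the unblinding. Record all other reactions on a separate form that stays masked until data lock and then supplies the 3.6.1 outcome.

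**Cost.** A few sentences and one form. For each patient reported, the treating team is unblinded, as is any outcome-collecting investigator who reads that patient's record, so transfusion decisions and complication grading are no longer masked for that patient. For serious events the chance that this happens at all is 0.08% with 20 infusions; for other hypersensitivity the documents give no rate. The primary outcomes are laboratory measurements and do not depend on this masking.
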